17.4 Analysis of other primary outcomes

The other primary outcomes, namely HIV provider willingness to prescribe XR-NTX (Aim 1) and Patient acceptance of XR-NTX. (Aim 2) are both results from pre-randomization surveys based on convenience samples. We will present descriptive statistics for all such survey results.

¹ The rationale for this fine point follows: Consider a pilot-study site that recruited its only patient one day after the trial starts. If, in our subsequent bootstrap simulation, we ignored this site's 364-day waiting period after the only enrollment, it would look like the site inter-arrival time for all recruitments was only 1 day -- clearly a misrepresentation of that site's behavior. This means we cannot ignore the final waiting time. Now consider another site that waits 364 days before its only recruitment. If we consider the final (1-day) waiting time to trial's end to terminate in an enrollment, it will look in the bootstrap simulation like this site is recruiting much faster than it really did. So we can't ignore the final waiting time, but we can't assume it terminates in an enrollment, either. The solution of not ignoring the final waiting time, but also not allowing an enrollment at the end of it, better represents the behavior of both these types of sites in the subsequent bootstrap simulation.

17.5 Analysis of secondary outcomes

The pilot study is small and thus probably under-powered for hypothesis tests. Any conclusions arising from secondary analysis must be regarded as hypothesis-generating only, and need to be validated by independent data. We contemplate no adjustment for multiplicity.

Secondary outcomes will be analyzed as indicated in the italicized text describing each secondary endpoint.

HIV outcomes:

- a) Sustained HIV RNA viral suppression (plasma HIV viral load of < 200 copies/mL) at 16 weeks (*binary, laboratory assay*). *Chi-squared test of independence of sustained viral suppression on treatment assignment.*
- b) Change in CD4 count at 16 weeks following randomization compared with baseline (*count; laboratory measurement*). T-test.

1) Engagement in HIV Care:

- a) Change in the proportion of study participants prescribed ART within 16 weeks following randomization, compared to baseline (*binary; medical record abstraction*). *Each individual can be scored either 0 (not prescribed ART) or 1 (prescribed ART) at both baseline and follow-up, after which his or her outcome score will be the follow-up score minus the baseline score. Outcome scores will be analyzed via rank-based methods such as Wilcoxon rank-sum tests. Covariates can be considered via the cumulative logit model.*
- b) Proportion of participants taking 100% of prescribed ART doses in the past 3 days at 16 weeks for those prescribed ART at any point during the 16 week trial (*proportion; self-reported ACTG adherence measure*). *Chi-squared test comparing proportion to treatment assignment, for those prescribed ART.*
- c) Number of HIV primary care visits at 16 weeks (count, chart abstraction) *outcome scores will be analyzed via rank-based methods such as Wilcoxon rank-sum tests.*

2) Substance Use:

- a) Change in 30 day opioid abstinence (by ASI-lite self-report, TLFB and urine drug screen (UDS) confirmation) in the final 30 days of the 16 week trial compared to baseline (*binary; laboratory data and self-report*). *Analysis using rank-based methods as in outcome 2a.*
- b) Change in past 30day alcohol and other drug use by ASI-lite, TLFB, and UDS at 16 weeks, compared with baseline (*binary; laboratory data and self-report*). *Analysis using rank-based methods as in outcome 2a.*

3) Participant safety, as measured by:

- a) Change in liver enzymes between baseline and 16 weeks or last lab measurement (*continuous; laboratory assay*). *Analysis via paired t-test, or analysis of change via ordinary least squares.*
- b) Any fatal and non-fatal opioid overdose at 16 weeks (*binary; medical record abstraction and self-report*). *Chi-squared test or logistic regression.*
- c) Change in Concise Health Risk Tracking score at 16 weeks compared to baseline (*continuous; self-report*). *Analysis via paired t-test, or analysis of change via ordinary least squares.*
- d) Proportion of participants assigned to XR-NTX who develop precipitated opioid withdrawal.

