Aim 4: Assess the feasibility of integrating XR-NTX for opioid and alcohol use disorders into HIV clinics. Data collection during study start-up will inform selection of 2 HIV clinics to implement XR-NTX treatment. HIV providers and staff will be trained in detoxification and XR-NTX induction and management. HIV-infected subjects with untreated opioid and/or alcohol use disorders will be randomized to XR-NTX or TAU, followed by detoxification (if needed) and treatment induction. The primary outcomes are 1) treatment initiation (successful treatment initiation of XR-NTX or TAU within 4 weeks of randomization), and 2) retention on treatment condition at 16 weeks. Secondary outcomes include change in 1) HIV-1 RNA viral suppression, 2) Illicit drug and alcohol use, 3) HIV care engagement (receipt of ART, HIV visit adherence, ART adherence), and safety (percent with precipitated withdrawal, hepatotoxicity, or overdose).

Aim 4 Pilot Objective A: Estimate effect size point estimates for rate of treatment initiation and 16 week retention among HIV-infected patients with alcohol or opioid use disorders randomized to XR-NTX vs. TAU.

Aim 4 Pilot Objective B: Estimate effect size point estimates for secondary outcomes of HIV-1 RNA viral suppression, illicit drug and alcohol use, HIV care engagement, and safety among HIV-infected patients with alcohol or opioid use disorders randomized to XR-NTX vs. TAU.

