Conceptual Model. Substance use disorders impair patient engagement and retention in HIV care, contributing to gaps in the HIV care cascade (Gardner, McLees et al. 2011; Fleishman, Yehia et al. 2012). The CHOICES study seeks to compare office-based XR-NTX vs. TAU for treating opioid and/or alcohol use disorders in HIV-infected participants to improve engagement and retention in HIV treatment that leads to HIV viral suppression (Figure 4.1.1). Patient and provider attitudes, assessed in the pilot study, influence adoption of new treatment modalities (Rieckmann, Daley et al. 2007). The primary outcomes of the pilot study will be to assess critical implementation questions. The Consolidated Framework for Advancing Implementation Science suggests that patient, provider, and organizational attitudes are key inputs to adoption of new evidence-based technologies in healthcare settings (Damschroder, Aron et al. 2009). The proposed pilot study will assess HIV clinic provider and patient attitudes toward adoption of antagonist therapy as well as estimate treatment initiation and retention for participants randomized to XR-NTX vs. TAU. We will assess HIV virologic suppression and other key constructs in the causal pathway as secondary outcomes in the pilot study to obtain point estimates to inform development of a future multi-site clinical trial. Virologic suppression reduces HIV associated morbidity, prolongs survival, restores and preserves immunologic function and decreases HIV transmission (Department of Health and Human Services 2011). As shown in the conceptual model below, decreased use of opioids and alcohol and uptake of ART are proximal outcomes that will be assessed as secondary endpoints in the multi-site study. Most HIV-infected patients with alcohol and opioid use disorders who begin ART should be able to achieve virologic suppression if they continue in HIV care and adhere to ART (Cofrancesco et al., 2008; Hicks et al., 2007). In this model, successful treatment of alcohol and opioid use disorders is hypothesized as an important moderator of viral suppression. Previous research has shown that HIV-infected participants with a history of substance use treatment are more likely to use HIV primary care and receive ART (Bell et al., 2010; Knowlton et al., 2006; Loughlin et al., 2005; Strathdee et al., 1998). The model also includes other covariates that may be related to engagement in HIV primary care or substance use treatment.

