5.2 Secondary Objectives

Secondary objectives are to generate point estimates for comparing the effectiveness of XR-NTX vs. TAU in:

- 1) HIV outcomes, as measured by:
 - a) HIV-1 RNA viral suppression (plasma HIV viral load of ≤ 200 copies/mL) at 16 weeks compared with screening.
 - b) Change in CD4 count at the week 16 visit compared with screening.
- 2) Change in Substance Use:
 - a) Change in 30 day opioid abstinence (by Addiction Severity Index (ASI)-lite self-report, Timeline Follow Back (TLFB) and urine drug screen (UDS) confirmation) in the final 30 days of the 16 week trial compared to screening.
 - b) Change in past 30-day alcohol and other drug use by ASI-lite, TLFB, and UDS at week 16 week visit, compared to screening.

3) Engagement in HIV Care, as measured by:

- a)** Change in the proportion of participants prescribed ART within 16 weeks following randomization compared to baseline.
- b)** Proportion of participants taking 100% of prescribed ART doses in the past 3 days at 16 weeks for those prescribed ART at any point during the 16 week trial.
- c)** Number of HIV primary care visits at 16 weeks. Adherence to HIV clinic visits in the year after ART initiation predicts HIV disease progression and death (Park, Choe et al. 2007).

4) Participant safety, as measured by:

- a)** Change in liver enzymes between screening and week 16 visit.
- b)** Any fatal and non-fatal opioid overdose between screening and week 16 visit
- c)** Change in Concise Health Risk Tracking between screening and week 16 visit.
- d)** Proportion of participants assigned to XR-NTX who develop precipitated opioid withdrawal.

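### Section 17.5 does not commit to the XR-NTX versus TAU estimates that the secondary objectives call for, and one analysis it allows has no arm comparison

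*Protocol*

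**What the plan says.** **What is asked for.** Section 5.2 states: "Secondary objectives are to generate point estimates for comparing the effectiveness of XR-NTX vs. TAU in" the listed HIV, substance use, care engagement and safety outcomes. Aim 4 Objective B in Section 2.1 reads: "Estimate effect size point estimates for secondary outcomes of HIV-1 RNA viral suppression, illicit drug and alcohol use, HIV care engagement, and safety". Section 4.1 gives the use of these figures: "to obtain point estimates to inform development of a future multi-site clinical trial".

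**What is planned.** Section 17.5 sets the rule: "Secondary outcomes will be analyzed as indicated in the italicized text describing each secondary endpoint". The methods it then names are:

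- Viral suppression at week 16: "Chi-squared test of independence of sustained viral suppression on treatment assignment".
- CD4 change: a t-test, with nothing further specified.
- ART prescription: a follow-up minus baseline score, then "Outcome scores will be analyzed via rank-based methods such as Wilcoxon rank-sum tests". A cumulative logit model is offered as an option for covariates.
- Opioid abstinence and alcohol/other drug use: the same rank method, by a cross-reference to outcome 2a. As numbered there, 2a is the opioid outcome itself; the ART outcome must be meant.
- ART adherence: chi-squared. HIV visits: rank-sum. Overdose: chi-squared or logistic regression.
- Liver enzymes and CHRT: "Analysis via paired t-test, or analysis of change via ordinary least squares".

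On liver safety, Section 2.1 promises "safety (percent with precipitated withdrawal, hepatotoxicity, or overdose"), and Section 6.1 lists a percentage with transaminitis. Section 17.5 analyses only the change in enzymes, to week 16 or the last measurement.

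**The concern.** The secondary results are meant to feed the planning of a larger trial, which needs arm differences and their uncertainty. A list of tests does not secure either. Section 17.5 itself says that the pilot is probably under-powered for hypothesis tests, so p-values are the less useful product. The contrast with Section 17.3 is plain: for treatment initiation and retention it commits to maximum likelihood estimates with exact intervals.

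Two choices go further than leaving the estimate unstated. A paired t-test cannot answer a question about arms. A ranked difference of two 0/1 values discards which state a person was in and does not return a difference in proportions. A change in mean enzymes to one time point can also miss a transient rise, although a percentage was promised.

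**Working it through.** **Sample size behind the checks.** Section 17.5 gives no figure to reproduce; the nearest is the Table 17.2.1 row for 2 sites, 2.28 per site-month, limits of 50 participants and 12 months (n = 48; half-widths 0.21 and 0.22). Poisson accrual with mean 2.28 × 2 × 12 = 54.7, capped at 50, has a 20th percentile of 48. Exact binomial half-widths are 0.209 for 12/24 and 0.218 for 11/22 (after the table's 10% attrition). The row reproduces, and about 25 per arm is the right size to work with.

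**1. Paired t-test (liver enzymes, CHRT).** Assumptions: 25 per arm, correlation 0.5 between baseline and follow-up, unit SD, two-sided 5%, 4,000 replicates, paired test pooled over the arms.

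| Truth | Paired t-test | OLS of change by arm | ANCOVA |
|---|---|---|---|
| Both arms fall 0.5 SD, no arm difference | 93% | 5% | 5% |
| Arms move +0.5 and −0.5 SD (difference 1 SD) | 3% | 94% | 98% |

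Running the paired test within each arm would not help: it gives two before-after p-values and still no contrast. The OLS columns assume an arm term, which Section 17.5 does not write down.

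**2. The −1/0/+1 score (three outcomes).** The four possible histories score as follows: off then on, +1; on then off, −1; on throughout, 0; never on, 0. Anyone positive at baseline cannot score +1. Section 4.1 reports 60% on ART at baseline in one cohort. With that mix, only 0.40 × 25 = 10 per arm could show uptake.

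Simulation with assumed ART start of 40% versus 80% among those off ART and 5% stopping in each arm:

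- 60% on ART at baseline: power 23% for rank-sum, 37% for a comparison stratified by baseline (Cochran-Mantel-Haenszel).
- 30% on ART at baseline: 50% and 66%.
- No effect, same baseline rate in both arms: both reject in about 5%.
- No effect, but baseline ART set at 70% versus 50% between arms: 16% and 5%.

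**3. CD4 change score.** With equal SDs and correlation ρ, the variance of the arm difference is proportional to 2(1 − ρ) for the change score and 1 − ρ² for ANCOVA. The ratio is 2/(1 + ρ).

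| ρ (assumed) | Variance ratio | 95% half-width, change (SD) | 95% half-width, ANCOVA (SD) |
|---|---|---|---|
| 0.3 | 1.54 | 0.66 | 0.53 |
| 0.5 | 1.33 | 0.55 | 0.48 |
| 0.7 | 1.18 | 0.43 | 0.40 |
| 0.8 | 1.11 | 0.35 | 0.33 |

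**4. Week-16 suppression.** Sections 5.2 and 8.2 define it relative to screening, yet the named chi-squared test uses no earlier value. Section 12.6 has HIV RNA drawn following randomization, so one exists.

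**5. Who counts for opioid outcomes.** Section 7.1 admits opioid and/or alcohol use disorder, and Section 17.5 states no restriction for opioid abstinence. If half the sample had alcohol use disorder only and no opioid use (assumed), a risk difference of 0.30 among the rest would appear as 0.5 × 0.30 = 0.15.

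**6. What an estimate would look like.** The unadjusted 95% half-width of a risk difference at 25 per arm is 1.96 × √(2p(1 − p)/25): 0.28, 0.25 and 0.22 at p = 0.5, 0.7 and 0.8. In a half-sized subset at p = 0.5 it is 1.96 × √(0.5/12.5) = 0.39.

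**The case against.** A reader might infer that the plan yields no arm effects at all. It does not go that far. Chi-squared and rank-sum tests compare arms; logistic regression, the cumulative logit model and OLS with an arm term can each give an effect. For ART prescription, the mean score in each arm is the change in proportion named in the objective, and naming a test does not forbid reporting the difference in means. A separate statistical analysis plan may add estimates. All this stands, and it limits the point to a missing commitment.

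Nor does every binary outcome become a score: suppression, ART adherence and overdose stay binary. Nor are the safety changes confined to a paired t-test, since OLS is the stated alternative.

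A reader might also infer that omitting the baseline biases the comparison. Under 1:1 randomization it does not; the 16% rejection above comes from an imposed imbalance, and with equal baseline rates the rank test rejects in about 5%. The precision gain depends on an assumed ρ.

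The dilution point rests on an assumed alcohol-only share and on Section 17.5 being silent about the analysis set, which a later plan could settle. Liver events are not wholly uncovered: clinically significant laboratory findings are adverse events (Section 22.1) and are tabulated by arm (Section 17.8). The 5-fold enzyme limit in Section 7.2 is an entry criterion, so it cannot be read as the protocol's definition of on-study hepatotoxicity.

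Finally, acceptability and feasibility are the primary goal. With about 25 per arm, adjusting for several covariates at once would be unstable.

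**Conclusion.** The concern holds as a mismatch between objective and method. Sections 2.1 and 5.2 require arm-versus-arm point estimates; Section 17.5 names mainly tests and no effect measure or interval. The clearest defect is the paired t-test option for liver enzymes and CHRT, because following it cannot answer the objective whatever the data show. The ranked scores for three outcomes come next: they merge two different histories and give no risk difference. The unadjusted CD4 change score and the suppression test without an earlier value are matters of precision only, with a variance ratio of 1.18 to 1.54 at ρ from 0.7 to 0.3.

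The correlations, effect sizes and alcohol-only share are assumptions, since the protocol gives none of them; the 60% ART figure is borrowed from a cohort it cites. The consequence is moderate, because Section 17.5 already labels these analyses hypothesis-generating, and the fix does not change that.

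**What to change.** In Section 17.5:

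- Delete the paired t-test option.
- Analyse CD4, AST/ALT (log scale if skewed) and CHRT by ANCOVA on arm and the pre-treatment value; report the adjusted difference with a 95% interval. Because HIV RNA and CD4 are drawn following randomization, require that the value used predates the assigned treatment.
- For suppression, ART prescription and abstinence, report between-arm risk differences with 95% intervals, adjusted or stratified for the pre-treatment value only, given about 25 per arm.
- Report opioid outcomes among participants with opioid use disorder and alcohol outcomes among those with alcohol use disorder, at least alongside the full-sample result.
- Report by arm the percentage with hepatotoxicity or transaminitis promised in Sections 2.1 and 6.1, using all AST/ALT values from weeks 1 to 16. The sponsor should define the cut-off, as an analysis summary only.
- Correct the cross-reference to outcome 2a.

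The cost is wording and slightly more modelling. The variables are already collected and the sample size is unchanged. The disorder-specific intervals will be wide.

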An open-label implementation study evaluating XR-NTX treatment of alcohol dependence in primary settings demonstrated that integrating XR-NTX was feasible and associated with marked reductions in drinking days, heavy drinking days, and improved abstinence (Lee, Grossman et al. 2010; Lee, Grossman et al. 2012). Partici-

pants completed a median 38 weeks (range 16-72) of treatment, with a median 8 monthly injections (range 4-15).

Naltrexone in HIV-infected populations. The CHOICES study is the first to assess XR-NTX in an HIV-infected clinic-based population. Daily oral naltrexone has been safely used to treat alcohol and opioid use disorders in HIV-infected persons. Tetrault, et al. assessed changes in liver enzymes and HIV biomarkers in 114 HIV-infected U.S. Veterans 365 days before, during, and 365 days after treatment with oral naltrexone (Tetrault, Tate et al. 2012). Thirty-two percent of participants had opioid dependence, 89% had a history of alcohol dependence, 53% were coinfecting with hepatitis C, and 52% received antiretroviral therapy during naltrexone treatment. Participants were prescribed naltrexone for a median 49 days (interquartile range 30-83 days). Mean AST and ALT levels decreased during and after naltrexone treatment. Two of 114 participants (1.8%) experienced mild liver enzyme elevations during naltrexone treatment, less than 5-times the upper limit of normal, which resolved upon treatment discontinuation. Mean HIV RNA levels decreased after naltrexone treatment and mean CD4 count remained stable throughout. This study suggests the risk of hepatotoxicity is minimal in HIV-infected participants treated with naltrexone, and that there are no adverse immunologic or virologic effects of treatment.

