The pilot study consists of a two-arm, 16-week, open-label, randomized, pilot trial of XR-NTX vs. TAU for treatment of opioid and alcohol use disorders in HIV-infected patients. Study participants are individuals with HIV infection and alcohol and/or opioid use disorders and who have received patient-centered information about both antagonist and agonist treatment options for alcohol and opioid use disorders. During screening, eligible participants will be surveyed regarding their attitudes about opioid antagonist therapy for opioid and alcohol use disorders (Aim 2). We will track the rate of participant recruitment (i.e., no more than 50 participants over no more than 12 months) to estimate duration of study recruitment required for a multisite study (Aim 3). Eligible patients are randomized in a 1:1 ratio to receive XR-NTX vs. TAU (Aim 4). Participants with both alcohol and opioid use disorders will be categorized by their self-reported substance of choice. XR-NTX (provided as Vivitrol®) will be administered by HIV clinic providers as a monthly intramuscular injection. Study visits will occur every 4 weeks for collection of blood and urine samples, safety, and other assessments. Primary outcomes of treatment initiation within 4 weeks of randomization, and retention at 16 weeks (maximum of 4 XR-NTX injections) and analyzed by intent-to-treat will be assessed. Secondary outcomes assessed at 16 weeks include change in 1) HIV-1 RNA viral suppression, 2) illicit drug and alcohol use, 3) HIV care engagement (receipt of ART, HIV visit adherence, ART adherence), and safety (percent with precipitated withdrawal, overdose, transaminitis).

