8.2 Secondary Outcome Measures

1) HIV outcomes:

- a) HIV-1 RNA viral suppression (plasma HIV-1 RNA pcr < 200 copies/mL) at 16 weeks compared with screening (binary, laboratory assay).
- b) Change in CD4 count at 16 weeks following treatment initiation compared with screening (count; laboratory measurement).

2) Substance Use:

- a) Change in 30 day opioid abstinence (by Addiction Severity Index (ASI)-lite self-report, Time-Line Follow-Back (TLFB) and urine drug screen (UDS) confirmation) in the final 30 days of the 16 week trial compared to screening (binary; laboratory data and self-report).
- b) Change in past 30-day alcohol and other drug use by ASI-lite, TLFB and UDS at week 16 visit, compared to screening (binary; laboratory data and self-report).

3) Engagement in HIV Care:

- a) Change in the proportion of participants prescribed ART within 16 weeks following randomization, compared to baseline (binary; medical record abstraction).
- b) Proportion of participants taking 100% of prescribed ART doses in the past 3 days at 16 weeks for those prescribed ART at any point during the 16 week trial (proportion; self-reported ACTG adherence measure).
- c) Number of HIV primary care visits at 16 weeks (count, chart abstraction).

4) Participant safety:

- a) Change in liver enzymes between screening and week 16 visit (laboratory assay).
- b) Any fatal and non-fatal opioid overdose between screening and week 16 (binary; medical record abstraction and self-report).
- c) Change in Concise Health Risk Tracking score between screening and week 16 visit (continuous; self-report).
- d) Proportion of participants assigned to XR-NTX who develop precipitated opioid withdrawal.

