12.6 Clinical Laboratory Tests

Trained staff will be responsible for collecting and processing biologic specimens. Local laboratories at participating pilot sites will be used to conduct laboratory tests. Laboratories must be accredited by the College of American Pathologists (CAP) or equivalent, and participate in the Clinical Laboratory Improvement Act of 1998 (CLIA) or equivalent evidence of laboratory certification. Laboratories will provide reference ranges and proof of laboratory certification.

HIV-1 RNA PCR: will be drawn following randomization, and at 4, 8, 12, and 16 week follow-up visits (or end-of-medication/end-of-treatment if medication or TAU intervention stopped early) for outcomes assessment.

CD4 Count (T-helper cells): will be drawn following randomization and at 4, 8, 12, and 16 week visits (or end-of-medication/end-of-treatment if medication or TAU intervention stopped early) for secondary outcomes assessment.

Peripheral Blood Mononuclear Cells (PBMCs): For all participants, we will collect 4 CPT tubes for PBMC analysis following randomization and at the Week 4 visit or the first blood draw following study drug initiation. PBMC analysis will be conducted in a related NIH application to assess the effects of opioid blockade on TLR mediated immune responses. Samples must be drawn during CTN-0055 study implementation, but may be analyzed at a later time.

Safety labs: AST, ALT, CBC, INR, and urine pregnancy test (for females) will be performed to help determine eligibility at screening. Receipt and review of laboratory test results is necessary before confirming eligibility, conducting randomization and starting study medication. Results of laboratory tests conducted within 30 days prior to randomization (e.g., collected as part of routine detoxification admission) will be acceptable.

Liver profile: (AST, ALT, INR) will be repeated 1 week after study treatment initiation and at 4, 8, 12, and 16 week visits (or end-of-medication/end-of-treatment if medication or TAU intervention stopped early).

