22.9 Participant Withdrawal

The study medical clinician must apply his/her clinical judgment to determine whether or not an adverse event is of sufficient severity to require that the participant is withdrawn from further study medication administration. Extended-release naltrexone will be discontinued in participants with evidence of clinically significant deterioration in hepatic function and/or acute hepatitis, as assessed by the study clinician. The study medical clinician should consult with the site principal investigator, the lead investigator and/or Medical Monitor as needed. If necessary, a study medical clinician may suspend any trial treatments and institute the necessary medical therapy to protect a participant from any immediate danger. A participant may also voluntarily withdraw from treatment due to what he/she perceives as an intolerable adverse event or for any other reason. If voluntary withdrawal is requested, the participant will be asked to complete an end-of-medication visit to assure safety and to document end-of-medication outcomes and will be given recommendations for medical care and/or referrals to treatment, as necessary.

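### The overviews promise the percent with hepatotoxicity or transaminitis, but the outcome as defined is a mean change in liver enzymes to one final value, which can miss transient elevations

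*Protocol*

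**What the plan says.** Two descriptions of liver safety stand in the Protocol.

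- **As a percentage.** Aim 4 in Section 2.1 lists "safety (percent with precipitated withdrawal, hepatotoxicity, or overdose". Section 6.1 lists "safety (percent with precipitated withdrawal, overdose, transaminitis".
- **As a change.** Section 8.2 has "Change in liver enzymes between screening and week 16 visit (laboratory assay", and Sections 5.2 and 17.2 agree with it. Section 17.5 has "Change in liver enzymes between baseline and 16 weeks or last lab measurement", labels it continuous, and analyses it by paired t-test or by ordinary least squares on the change.

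Section 12.6 says that the liver profile "will be repeated 1 week after study treatment initiation and at 4, 8, 12, and 16 week visits", with a further sample at an end-of-medication or end-of-treatment visit when treatment stops early. Section 22.9 states "Extended-release naltrexone will be discontinued in participants with evidence of clinically significant deterioration in hepatic function". Section 9.7 keeps participants in follow-up for the study duration unless they withdraw consent or are removed.

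Precipitated withdrawal is worded the same way throughout: "Proportion of participants assigned to XR-NTX who develop precipitated opioid withdrawal".

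**The concern.** A percent with an event and a mean change to a final value answer different questions, and the Protocol commits to both under one outcome. The percentage asks how many people had a liver problem at any time. The change asks where the group's average stood at the end.

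The difference matters because drug-related elevations may be transient. In the oral naltrexone study of HIV-infected veterans cited in Section 4.1, the elevations were "less than 5-times the upper limit of normal, which resolved upon treatment discontinuation", while mean AST and ALT fell during and after treatment. A mean-change outcome applied to that study would have reported improvement and shown neither case.

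The pilot is described as the first assessment of XR-NTX in an HIV clinic population, and safety point estimates for a multi-site trial are a stated objective. An outcome that cannot count cases serves that purpose poorly.

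**Working it through.** **Inputs from the Protocol.** At most 50 participants randomised 1:1, so about 25 per arm (Sections 6.1, 6.2). Liver tests after treatment starts: weeks 1, 4, 8, 12 and 16 (Sections 10.1, 12.6). Entry is barred above 5 times ULN (Section 7.2). Elevations in the cited study: 2 of 114.

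**The Protocol's own figure.** 2/114 = 1.75%, which agrees with the stated 1.8%.

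**Share of results used.** For a completer, the outcome takes one of five scheduled post-treatment values. Four of five, 80%, do not enter it.

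**What each definition reports (assumed values, for illustration).** Take 25 participants in the XR-NTX arm, all at 1 times ULN before treatment. Three rise to 6 times ULN at week 4 and are back at 1 by week 16.

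- Mean change to week 16: (3 × 0 + 22 × 0)/25 = 0.0 times ULN.
- Percent with any post-baseline value above 5 times ULN: 3/25 = 12% (exact 95% CI 2.5% to 31.2%).

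**Effect of the last-laboratory wording.** Suppose the same three stop treatment at the peak and have an end-of-medication sample then. If that sample is the value analysed, the mean change is 3 × (6 − 1)/25 = 0.6 times ULN. If the week 16 sample is used, it is 0.0. Section 17.5 does not say which counts when both exist.

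**Reference value.** Sections 5.2, 8.2 and 17.2 measure from screening and Section 17.5 from baseline. The assessment table in Section 10.1 schedules the pre-treatment liver test at screening only, so the two labels may mean the same sample, but the text should say so.

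**Precipitated withdrawal.** Section 15.4 records it after each injection. Section 17.2 assumes 10% attrition before initiation. On that figure about 25 × 0.90 = 22.5 of 25 are injected, and the all-assigned rate is 0.90 times the rate among the injected: 20% would read as 18%. Any further dilution depends on the share of participants with alcohol use disorder only, which the Protocol does not give. At assumed shares of 25%, 50% and 75% the factor would be 0.675, 0.45 and 0.225.

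**The case against.** The strongest reply is that a serious liver signal is reported elsewhere. Section 22.1 makes a laboratory finding an adverse event when the study clinician considers it clinically significant. Section 19.3.1 requires every adverse event to be entered, and Section 17.8 tabulates affected participants by arm. A participant whose XR-NTX is stopped under Section 22.9 has in effect already met that test. This stands. A reader might infer that elevations leading to discontinuation drop out of the trial's reporting; they do not. They can drop out of this one secondary outcome.

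The reply leaves a gap, though. The adverse event route rests on clinical judgement in an unblinded study (Section 9.8), and the severity scale in Section 22.6 has no laboratory grades. Elevations judged not clinically significant are counted nowhere as cases.

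It is also fair to say that a resolved peak does not always score zero. If no later sample exists, the last-laboratory wording may keep the elevated value. That makes the loss possible rather than certain, and adds an ambiguity of its own.

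Three further inferences are tempting and unsupported.

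- Applying 2/114 to 25 participants gives 1 − (112/114)^25 = 36% for at least one elevation. This is not a chance of hidden hepatotoxicity: those cases were mild, below 5 times ULN, and on the oral formulation.
- Nothing suggests that the outcomes were chosen to favour XR-NTX. Section 17.5 calls the secondary analyses hypothesis-generating.
- The withdrawal denominator is not an error. It is consistent, follows assignment, and describes one arm only. The naloxone challenge in Section 9.3.3.2 depends on recent opioid use rather than diagnosis, so participants enrolled for alcohol use disorder cannot all be assumed free of risk.

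**Conclusion.** The point holds in a limited form. The Protocol promises a percentage with liver toxicity and then defines only a continuous change to a final value. For completers, 80% of the scheduled post-treatment liver results do not enter that outcome, a transient rise can contribute about zero, and a mean can hide individual cases. The loss is an objective incidence measure by arm; clinically significant elevations remain visible as adverse events.

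The 12% against 0.0 contrast rests on assumed values and shows the mechanism, not an expected rate. The disagreement between sections, the unused visits and the undefined last value need no assumption. No sample size or precision figure is affected.

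For precipitated withdrawal, the only dilution that the Protocol supports is a factor of about 0.90. A second denominator would be a useful optional display.

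**What to change.** Reconcile the Aim 4 summary and Section 6.1 with Sections 5.2, 8.2, 17.2 and 17.5:

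- Define the liver safety outcome as the worst post-baseline AST and ALT at any visit through week 16, in multiples of ULN. Report number and percent per arm by category.
- Include a category above 5 times ULN. The Protocol's own entry limit excludes anyone above it at screening, so a value there is a new crossing. Lower categories should be read beside the screening category, since participants may enter with raised enzymes.
- Keep the change to week 16 as descriptive. State whether screening or baseline is the reference, and which value counts when both an end-of-medication and a week 16 sample exist.
- Optionally, report precipitated withdrawal among injected participants with opioid use disorder or recent opioid use, next to the all-assigned figure.

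The cost is revised outcome wording, a choice of categories and one or two table rows. No new visits, tests or participants are needed.
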